7.2. STUDY PHASES

The study consists of 3 phases:

Visit 1: Preoperative phase (screening)

- ❖ Patient Screening (Check eligibility)
- ❖ Signed ICF
- ❖ Gathering Patient Information as Demographic, Vital Signs, BMI, Physical Examination, Medical History, Concomitant medications
- ❖ Laboratory Investigations (Hb, PLt count, APTT, INR, SGPT, SGOT, Serum Albumin, Serum Bilirubin, serum creatinine, Creatinine clearance, Random blood sugar)
- ❖ Patients main complaint (Knee, Hip)

Operative phase (Day 0)

Patient Data to be collected:

- ❖ Type , Date of surgery
- ❖ Type of anaesthesia
- ❖ Patient position
- ❖ Type of prosthesis
- ❖ Blood transfusion

Start of IMP administration.

APTT 4 & 8 hours after IMP administration

Visit 2: Post operative phase (Follow-up 1 (Day 1))

- ❖ Assessment of bleeding
- ❖ Type of blood transfusions
- ❖ Assessment of DVT
- ❖ Routine bilateral compression Doppler (confirmation for DVT)
- ❖ Assessment of PE
- ❖ Spiral CT (confirming PE)
- ❖ IMP administration
- ❖ Laboratory investigations (Hb%, Platelets count)
- ❖ APTT

Assessment will be done in the hospital, as post-operative period before discharge from hospital.

Visit 3: Follow-up 2 (Day 8)

- ❖ Assessment of bleeding
- ❖ Type of blood transfusions
- ❖ Assessment of DVT
- ❖ Routine bilateral compression Doppler (confirmation for DVT)
- ❖ Assessment of PE
- ❖ Spiral CT (confirming PE)
- ❖ IMP administration
- ❖ Laboratory investigations (Hb%, Platelets count)
- ❖ APTT

Assessment in day 8 will be done from outpatient clinic in most patients.

Visit 4: Follow-up 3/ End of Study (Day 15)

- ❖ Assessment of bleeding
- ❖ Type of blood transfusions
- ❖ Assessment of DVT
- ❖ Laboratory Investigations
- ❖ Routine bilateral compression Doppler (confirmation for DVT)
- ❖ Assessment of PE
- ❖ Spiral CT (confirming PE)
- ❖ APTT
- ❖ End of Study

Assessment in day 15 will be done from outpatient clinic.

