15.1. DATA MANAGEMENT

All data collected in this study will be entered manually by data entry team on Oracle database specially designed to meet the needs of clinical trials prepared by Minapharm.

Edit checks will be run on the data and queries issued as needed and queries will be resolved. Full quality control data verification will be done and then data will be declared clean. Database will be locked after Minapharm medical department approval.

Extraction of data for statistical analysis will be done once database lock occurs. All data collected in the paper CRFs will be documented in subject data listings and summarized in tables, as appropriate.

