16.2. Reporting Period

For serious adverse events, the reporting period to Sponsor or its designated representative begins from the time that the subject provides informed consent, which is obtained prior to the subject's participation in the study, i.e. prior to undergoing any study-related procedure and/or receiving investigational product, through and till the end of the Follow Up Period as specified in the study protocol.

Any serious adverse event occurring any time after the reporting period must be promptly reported if a causal relationship to investigational product is SUSPECTED.

16.3. Adverse Event (AE):

An adverse event is any untoward medical occurrence in a clinical investigation subject administered a product or medical device; the event need not necessarily have a causal relationship with the treatment or usage.

Examples of adverse events include but are not limited to:

- Abnormal test findings
- Clinically significant symptoms and signs
- Changes in physical examination findings
- Hypersensitivity
- Progression/worsening of underlying disease

Additionally, they may include the signs or symptoms resulting from:

- Drug overdose
- Drug withdrawal
- Drug abuse
- Drug misuse
- Drug interactions
- Drug dependency
- Extravasation

Exposure during pregnancy
Drug Quality Defect that has impact on the patient safety

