2.3 The Follow-Up Phase

During this phase which is approximately 15 days, PE (Pulmonary Embolism) which is confirmed by spiral CT chest, any new DVT appears also to be confirmed by Doppler ultrasound, Bleeding assessment, APTT will be done on days 1, 8 & 15, concomitant medications, Hospital stay and any adverse event data will all be recorded

3 Study Objective:

3.1 Primary Objectives:

- To evaluate the efficacy of Subcutaneous Thrombexx® ampoules (r-Hirudin RB variant 15 mg) in DVT prophylaxis post major orthopedic operations

3.2 Secondary Objectives:

- To evaluate the safety of Subcutaneous Thrombexx® ampoules (r-Hirudin RB variant 15 mg) in DVT prophylaxis post major orthopedic operations in terms of serious bleeding.
- Predictive factors; baseline characteristics, Thrombexx® dose, duration and concomitant medications.
- Study population demographics and characteristics.

4 Study Outcome Measures:

4.1 Primary Endpoints:

- Primary end points included new onset symptomatic thrombosis requiring medical or surgical intervention or death due to thrombosis defined as fatal PE, ischemic stroke, mesenteric thrombosis, or myocardial infarction.
- The number of clinical PE events will be measured by spiral CT
- Mean changes in APTT where it will be done before first dose, 4 & 8 hours after first dose then on days 1,8,15 post operatively

4.2 Secondary Endpoints:

- **Major Bleeding:** was defined as clinically evident hemorrhage associated with a hemoglobin decrease ≥ 2 g/dL that leads to a transfusion of ≥ 2 units of whole blood or packed red cells outside of the perioperative period (time from the start of the surgery or procedure and up to 12 hours after), or hemorrhage that is intracranial, retroperitoneal, or into a prosthetic joint.

- Number of any reported (AE) or (SAE) during the study duration.

5 Study Population

This is a prospective study, it is important to have a well-defined study population in place prior to the start of the study. Study populations should be defined using specific inclusion and exclusion criteria, which will be used to evaluate a potential subject's ability to participate in the study.

5.1 Recruitment strategy:

It is essential that the recruitment process take into account factors that will optimize the type and number of participants enrolled in the study while minimizing time and expense. Failure to meet target accrual goals can affect the "power" of a study, making it less successful in providing quality results.

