8.2 Analyses variables

8.2.1 Primary analysis variables:

- Proportion of patients experienced new onset symptomatic thrombosis
- The number of clinical PE (Pulmonary Embolism) events will be measured by spiral CT

8.2.2 Secondary analysis variables:

- Number of adverse events recorded
- Proportion of patients experienced major bleeding

8.2.3 Statistical Method:

Descriptive analysis:

All statistical tests used a significance level of $P=0.05$, two tailed tests were performed for all analyses used statistical testing.

Descriptive analysis for quantitative data will include count, mean with 95% CI, standard deviation, median, minimum and maximum. For qualitative categorical variables; frequency and percentage and 95% confidence interval will be applied.

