9.3 Secondary End Point

Table 11 Proportion of patients experienced major bleeding

		Day 1	Day 8	Day 15	p-value
Assessment of Bleeding:	Normal, N (%)				
	Abnormal, N (%)				
Type Of Blood Transfusions:	Whole Blood, N (%)				
	RBCs, N (%)				
	Platelets, N (%)				
	Plasma, N (%)				

Table 12 *Number and percent of Adverse Event among treatment groups*

	N = 100	p-value
Total No of AE, N (%)		
AE1, N (%)		
AE2, N (%)		
AE3, N (%)		

Table 13 *Number and percent of Serious Adverse Event among treatment groups*

	N = 100	p-value
Total No of SAE, N (%)		
SAE1, N (%)		
SAE2, N (%)		
SAE3, N (%)		

Table 14 *Percent Change in mean Hb%*

	Screening	Day 1	Day 8	Day 15	p-value
Hb%, (mean ± SD)					
% change					
p-value					

Table 15 *Percent Change in mean Platelets count*

	Screening	Day 1	Day 8	Day 15	p-value
Platelets count, (mean ± SD), x 10³/μL					
% change					
p-value					

Table 16 *Percent Change in mean Systolic BP*

	Screening	Day 0	Day 1	Day 8	Day 15	p-value
Systolic BP, (mean ± SD), mmHg						
% change						
p-value						

Table 17 *Percent Change in mean Diastolic BP*

	Screening	Day 0	Day 1	Day 8	Day 15	p-value
Diastolic BP, (mean ± SD), mmHg						
% change						
p-value						

Table 18 *Percent Change in mean Sitting Pulse Rate*

	Screening	Day 0	Day 1	Day 8	Day 15	p-value
Sitting Pulse Rate, (mean ± SD), beats /min						
% change						
p-value						

Table 19 *Percent Change in mean Oral Temperature*

	Screening	Day 0	Day 1	Day 8	Day 15	p-value
Oral Temperature, (mean ± SD), °C						
% change						
p-value						

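### The SAP summarises post-baseline haemoglobin only as a group mean, so falls of at least 2 g/dL that miss the full major-bleeding definition are counted in no table

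*SAP*

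**What the plan says.** The secondary objective is safety in terms of serious bleeding (Protocol 5.2, SAP 3.2). The matching analysis variable in SAP 8.2.2 is a patient-level one: "Proportion of patients experienced major bleeding". Outside the critical sites, the definition in SAP 4.2 needs clinically evident haemorrhage with a "hemoglobin decrease ≥ 2 g/dL that leads to a transfusion of ≥ 2 units of whole blood or packed red cells", the transfusion falling outside the perioperative period.

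The tables that bear on haemoglobin or bleeding are these:

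- **Table 6** gives the mean and SD at screening only.
- **Table 14**, headed "Percent Change in mean Hb", covers Screening, Day 1, Day 8 and Day 15. Its rows are mean with SD, percent change and p-value.
- **Table 11**, for major bleeding, has a row "Assessment of Bleeding" split into normal and abnormal, and rows for the type of blood product, at Days 1, 8 and 15. It has no row for haemoglobin or for the number of units.

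Protocol 7.2 names haemoglobin at the Day 1 and Day 8 visits: "Laboratory investigations (Hb%, Platelets count". For Day 15 it lists laboratory investigations without saying which.

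**The concern.** Bleeding is the named safety risk, and bleeding harm falls on a few patients. A group mean averages those few with everyone else. Recovery after surgery in the other patients, and transfusion in the patients who bled, both push the mean upward.

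A patient who loses 3 g/dL and receives no blood or one unit does not meet the transfusion route of the definition. The size of that fall then contributes only to an average. The haemoglobin table could show no change, or even a rise, while several patients had large falls on treatment. The bleeding-safety section would then look cleaner than the data collected. With no comparator arm, nothing else in the design would expose this.

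**Working it through.** The documents give no haemoglobin figure to reproduce. Their one sample-size calculation concerns DVT incidence and has no bearing here. From the documents: N = 100 (SAP table shells and 8.1) and the 2 g/dL component (SAP 4.2).

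Assumptions, not in the documents: SD of the within-patient change from Day 1 to Day 8 of 0.8, 1.0 or 1.5 g/dL; five patients with an extra 3 g/dL fall; baseline mean 10 to 14 g/dL; a two-sided 5% paired t-test. The SAP puts a p-value in Table 14 but names no test.

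**1. Movement of the mean.** 5 × 3 / 100 = 0.15 g/dL. As a percent change this is 0.15/14 = 1.1% to 0.15/10 = 1.5%.

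**2. Chance that the test shows a fall.** The five falls also widen the spread. The total SD is √(SD² + 3² × 0.05 × 0.95) = √(SD² + 0.4275), and the standard error is that divided by √100. The last two columns are from 20,000 simulated trials per SD.

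| SD of change | Total SD | Standard error | 0.15 / SE | Significant fall | Same, if transfusion restores 2 g/dL |
|---|---|---|---|---|---|
| 0.8 | 1.03 | 0.103 | 1.45 | 25% | 8% |
| 1.0 | 1.19 | 0.119 | 1.26 | 19% | 6% |
| 1.5 | 1.64 | 0.164 | 0.92 | 12% | 5% |

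With restoration, the mean moves by 5 × 1 / 100 = 0.05 g/dL. If instead all patients recover by 0.5 g/dL on average (SD 1.0) and the five still have their extra 3 g/dL fall, the mean rises by 0.50 − 0.15 = 0.35 g/dL. A significant fall then appears in 0% of trials and a significant rise in 87%.

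**3. Can the count be recovered from Table 14?** No. Take a mean fall of 1 g/dL and a normal model. The share falling at least 2 g/dL is 1 − Φ((2 − 1)/SD): 2.3% at an SD of 0.5, 15.9% at 1.0 and 25.2% at 1.5. The table reports the SD of the values at each visit. The SD of the change is not shown, so the reader cannot tell these cases apart.

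**4. Precision of a count.** Exact (Clopper-Pearson) 95% intervals with N = 100 are 0 to 3.6% for 0 patients, 0.2% to 7.0% for 2, 1.6% to 11.3% for 5, and 4.9% to 17.6% for 10.

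**5. Background crossings.** The model has independent variation at Days 1, 8 and 15, scaled so that each change has the stated SD. It gives the share of patients who fall at least 2 g/dL from Day 1 to either later visit by variation alone.

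| SD of change | No true change | Recovery of 0.5 g/dL per interval |
|---|---|---|
| 0.8 | 1.2% | 0.1% |
| 1.0 | 4.1% | 0.8% |
| 1.5 | 15.4% | 6.4% |

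**The case against.** A reader might infer that 2 g/dL is the plan's own bleeding threshold. It is not. It counts only together with overt haemorrhage and at least two transfused units; critical-site bleeding is a separate route. A fall in haemoglobin after surgery need not be bleeding.

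A reader might also infer that late blood loss can go unreported. That is too strong, because several other routes exist:

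- Table 11 shows abnormal bleeding assessments and transfusions at Days 8 and 15.
- Protocol 16.3 gives "Abnormal test findings" as an example of an adverse event, so a fall can reach Table 12 or 13.
- Protocol 15.1 states: "All data collected in the paper CRFs will be documented in subject data listings and summarized in tables, as appropriate".
- SAP 8.2.3 states: "Descriptive analysis for quantitative data will include count, mean with 95% CI, standard deviation, median, minimum and maximum". An extreme value would therefore be visible.

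These routes stand, but each is partial. Table 11 gives no size of fall. Adverse-event capture depends on the investigator's judgement, with no haemoglobin criterion set. Listings are not a planned summary. A visit minimum shows one patient's level, not a change and not how many were affected.

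Two statistical objections also stand. The detection rates rest on assumed values and an assumed test. And a threshold count would not simply read 5 out of 100 in the example. For Day 1 to Day 8 the expected count is 5 × Φ(1/SD) + 95 × Φ(−2/SD), which is 5.1, 6.4 and 12.4 at SDs of 0.8, 1.0 and 1.5. At the largest SD most of the counted patients are background variation.

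**Conclusion.** The point holds as a gap in tabulation. Table 14 is the only table of post-baseline haemoglobin, it works on the group mean, and no table counts falls of at least 2 g/dL that miss the full major-bleeding definition. Under the stated assumptions, five extra 3 g/dL falls among 100 patients would give a significant fall in the mean only about 12% to 25% of the time, and less often after transfusion or with general recovery.

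The major-bleeding endpoint is unaffected. The documents do not support saying that such falls would go wholly unreported. In a single-arm trial a count of falls cannot be attributed to the drug either. It is still the better summary for a bleeding-safety objective, and the change is worth making before the analysis.

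**What to change.** Add to SAP Table 14, next to the mean, the number of patients, percentage and exact 95% CI for:

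- **(a)** a haemoglobin fall of at least 2 g/dL from Day 1 to any later scheduled value (Day 8 or Day 15), with the fall from screening shown separately so that surgical and early post-dose loss is visible;
- **(b)** such a fall from Day 1, or a red-cell or whole-blood transfusion recorded at Day 8 or Day 15. This keeps a transfused patient whose value has been restored.

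Measuring from Day 1 rather than from the previous visit matters: a loss of 1.5 g/dL in each interval totals 3 g/dL but would not count in either interval alone.

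Label the rows as a descriptive supplement to the unchanged major-bleeding endpoint, reported alongside it in the safety conclusion, with the mean change as supportive.

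Reconcile the documents on Day 15. The flow chart in Protocol 7.1 marks laboratory tests but no bleeding assessment. Protocol 7.2 lists a bleeding assessment but does not name haemoglobin. SAP Tables 11 and 14 have Day 15 columns for both.

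The cost is a few rows in one table, with no added visits. The Day 8 part uses data already planned; the Day 15 part depends on the reconciliation. The downside is background crossings: about 1% to 15% of patients with no true change, or 0.1% to 6% with a recovery of 0.5 g/dL per interval, for assumed SDs of 0.8 to 1.5 g/dL. The table note should say that the count is descriptive for this reason.

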9.4 Study Discontinuation

Table 20 Number and percent of causes of treatment discontinuations

		N = 100	p-value
Did the patient complete the study as per protocol?	Yes, N (%)		
	No, N (%)		
Reason for the discontinuation from study	Patient Withdrew Voluntarily		
	Adverse Event		
	Lost Follow-up		
	Death		
	Other Reasons		

